We will therefore secondarily conduct an economic evaluation to determine the relative incremental hospital cost of each fluid. To the extent that one fluid or the other reduces cost (assuming similar complication rates), the Clinic will be able to reduce cost by specifying the appropriate fluid without impairing quality.

Evidence that one fluid or the other causes few complications would be a strong quality indicator that the Clinic should standardize perioperative fluid selection.

Outcomes

1. **Primary:** Post-operative morbidity, as assessed by a composite outcome consisting of the following major complication components: renal, respiratory, infectious and hemorrhagic.
2. **Secondary:**
 - a. Acute kidney injury (AKIN criteria);
 - b. Economic evaluation.
3. **Tertiary:**
 - a) Blood transfusion;
 - b) Number of plasma electrolytes determinations;
 - c) Electrolyte replacement (i.e., administration of calcium, magnesium, potassium, or bicarbonate);
 - d) Post-operative nausea vomiting.
 - e) Myocardial Injury after Noncardiac Surgery
 - f) Cardiac complication

Methods

We propose an alternating intervention quality study comparing intraoperative fluid management with normal saline and lactated Ringer's solutions. This general approach to quality questions has been used at the Clinic and shown to produce more reliably clinical guidance than propensity-matched retrospective analyses.³⁷

This project will focus on colorectal and orthopedic surgery because these operations are conducted in physically distinct units that are normally staffed by small groups of anesthesiologists. Furthermore, most of the cases are substantial and require postoperative hospitalization. Both the anesthesia and surgical teams have agreed to the proposed project and representatives are co-investigators.

Protocol

We propose that all orthopedic and colorectal surgery operating rooms will alternate between using either normal saline or lactated Ringer's solution for 2-week periods. For example, the first period will use normal saline; the second will use lactated Ringer's, and so on for a maximum total of approximately 36 cycles. Thus, fluid choice will not be randomized on a per-patient or even per-period basis. Patients will not be informed of their group assignments, but will be told what fluids they received in the event they ask.

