There will be no other restriction on anesthetic management and practitioners will be free to use intravenous anesthetics and neuraxial analgesia per their preference. Intraoperative clinicians will not be blinded to type of crystalloid and will be free to use whichever fluid they deem preferable if clinically indicated. Normal saline will always be available for blood dilution. Crystalloid volume and timing will be determined by the anesthesia care team as usual. Other fluid, blood products, electrolyte replacement will be used at the discretion of anesthesia care team.

Measurements

All study outcomes will be obtained from electronic medical records including demographic and morphometric characteristics. Types of surgery will be characterized from ICD-9 codes using AHRQ Clinical Classifications Software. All routine anesthetic variables, including inspired oxygen fraction and expired carbon dioxide partial pressure, will be recorded per routine by our electronic anesthetic record-keeping system. Preoperative laboratory test, including but not limited to hemoglobin, hematocrit, BUN, creatinine, glucose, electrolytes and blood gas measurements, will be recorded. Transfusions will be recorded. Core temperature will be recorded, and patients will be kept normothermic per routine.

In colorectal surgery database, baseline risk of infection will be gathered evaluated using the Center for Disease Control (CDC) SENIC score, where one point each was assigned for ≥ 3 diagnoses, surgical duration ≥ 2 h, abdominal site of surgery, and the presence of a contaminated or dirty-infected wound.³⁸ The score will be slightly modified from its original form by our use of admission — rather than discharge — diagnoses.

Infection risk will be further quantified using the National Nosocomial Infection Surveillance System (NNISS), in which risk is predicted based on type of surgery, American Society of Anesthesiologists Physical Status score, and the duration of surgery.³⁹ Surgical wounds will be considered infected when they met the 1992 revision⁴⁰ of the CDC criteria for surgical wounds originally proposed in 1987.⁴¹ These data will be obtained from the Department of Colorectal Surgery registry and from orthopedic surgery departments, where they are recorded per routine.

Primary outcome

1. **One or more major complications**, including in-hospital mortality, renal (AKIN criteria 2+), respiratory, infectious, and hematological complications.

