Because the incidence and severity of the individual major complications vary considerably, we will analyze morbidities in a multivariate (one record per outcome per patient) analysis instead of a collapsed composite approach. A multivariate approach allows us to capture information regarding individual morbidities and the correlation between morbidities.

The average relative effect of lactated Ringer's solution versus saline will be assessed across the five categories of major complications using generalized estimating equations (GEE) 'distinct effects' model with an unstructured working correlation matrix.⁵¹ To assess heterogeneity of the fluid effect across components of the primary outcome, we will assess the treatment-by-component interaction in a distinct effects GEE model. We will assess whether the average component-specific treatment effect was equal to zero using an average relative effect test. However, if the baseline incidences are either quite different from each other or if some are very small (say < 1%), will instead use the common effect GEE test. All analyses will adjust for unbalanced potentially confounding baseline characteristics.

Secondary analysis

The economic evaluation will be conducted from the hospital/payer perspective to determine the optimal strategy for economic outcomes between the two interventions. The evaluation will determine the incremental costs between the two interventions; uncomplicated care and care of complications, as well as a combined incremental cost. An example analysis is listed below showing the incremental difference between the interventions for various outcomes for standard care and complications. A cost is assigned to each outcome and a total cost per patient calculated.

Standard Care - Example

	Intervention A	Intervention B	Incremental Dif.	Estimated Cost	Total Cost
LOS	1	0.8	0.2	100	20
Electrolyte Measures	10	8	2	10	20
Electrolyte Replacement	2	1	1	20	20
				Total Cost/pt	60

Complications - Example

	Intervention A incidence	Intervention B incidence	Incremental Dif.	Estimated Cost	Total Cost
MI	0.1	0.05	0.05	10,000	500
DVT	0.2	0.1	0.1	1000	100
Pneumonia	0.3	0.2	0.1	2000	200
				Total Cost/pt	800

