This study is designed to have about 90% power at the 0.05 significance level to detect a 20% relative decrease in major complications LR versus saline. We estimated the incidence of complications in the control group (saline) assuming that the two groups average out to the overall incidence. Sample size was calculated assuming a conservative correlation of 0.3 between outcomes. We estimated sample size using the MULTBINPOW SAS macro, which can estimate power for average relative effect GEE models given varying correlations and sample sizes (Mascha EJ Power Calculations for Tests on a Vector of Binary Outcomes (MULTBINPOW)).⁵¹ Cleveland Clinic Statistical Software Series 10 edn Cleveland; 2011: SAS program uses simulations to compute and display comparative power of several parallel-group multivariate tests for treatment effect on a vector of binary events.⁵² After accounting for 3 interim analyses and 1 final analysis, we will need to enroll a maximum of 8,548 patients for this study. If the Average Relative Effect analysis proves insufficient, we expect to nonetheless have > 99% power to detect a 20% relative increase in major complications in saline versus LR using either the collapsed composite or common effect GEE methods.

However, it is likely that the study would stop early. The table below provides boundary crossing probabilities for possible true underlying treatment effects: Null (no effect), Alternative (20% relative increase), half-way between the null and alternative, and 1.5 times the alternative effect. If the alternative hypothesis were true, the probability of crossing either the efficacy or futility boundary would be a cumulative 40% and 78% at interim analyses 2 and 3 (see “Alternative” row). Thus, there would be a 40% chance of stopping the study after N = 3,420 patients and 78% chance when N = 6,668 patients were enrolled if the alternative hypothesis is true. With an estimated 6,240 eligible patients available every year, we can expect this study to take a maximum of 1.37 years.

Expected Cumulative Boundary Crossing Probabilities (i.e., boundary crossing probabilities for either efficacy or futility)					
Effect*	Expected Crossing Stage	Boundary Crossing Probabilities			
		Interim 1	Interim 2	Interim 3	Final
Null	2.7	0.08	0.42	0.84	1.0
Alternative	2.7	0.09	0.40	0.78	1.0
½ Null, Alternative	3.0	0.06	0.28	0.63	1.0
Alt x 1.5	1.9	0.29	0.81	0.98	1.0

* True treatment effect in the population

Internal pilot study

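### The protocol does not fix one primary test: outcome definition, analysis section, switch rule and sample size point to three different ones

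*Protocol*

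**What the plan says.** All places are in the Protocol.

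- **Measurements, Primary outcome:** "One or more major complications, including in-hospital mortality, renal (AKIN criteria 2+), respiratory, infectious, and hematological complications". Taken literally, this is a collapsed composite.
- **Data Analysis, Primary analysis:** "we will analyze morbidities in a multivariate (one record per outcome per patient) analysis instead of a collapsed composite approach". The test is then named: "The average relative effect of lactated Ringer's solution versus saline will be assessed across the five categories of major complications". A switch follows, conditional on baseline incidences being far apart, or "if some are very small (say < 1%), will instead use the common effect GEE test".
- **Interim analyses:** four efficacy and futility boundaries are applied to the composite of major complications. The test that supplies the P value is not named.
- **Sample size:** N = 8,548 for about 90% power, obtained with a macro for average relative effect models. Then: "If the Average Relative Effect analysis proves insufficient, we expect to nonetheless have > 99% power to detect a 20% relative increase in major complications". The same sentence ends by naming the alternatives it has in mind: "using either the collapsed composite or common effect GEE methods".
- **Outcomes:** the composite is listed with only four components ("renal, respiratory, infectious and hemorrhagic"), without mortality. The other sections use five.

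**The concern.** A confirmatory trial needs one primary test that can be identified before the data are seen. Here a reader following the outcome definition would compare proportions with any event. A reader following the Primary analysis section would start with the average relative effect, then apply the switch rule to the protocol's own table and arrive at the common effect test. A reader following the Sample size section would return to the average relative effect, with two alternatives held in reserve.

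This would matter little if the three tests were near-equivalent, but they are not. The average relative effect gives each component one fifth of the weight. The other two are dominated by infection. On the tabulated incidences, infection is 23.76 / (0.53 + 1.75 + 2.34 + 23.76 + 2.55) = 23.76 / 30.93 = 77% of all component events. The choice of test can therefore decide both the final conclusion and whether a stopping boundary is crossed.

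**Working it through.** **Inputs.** From Sample size: saline incidences 0.59, 1.94, 2.60, 26.40 and 2.83% (mortality, renal, respiratory, infectious, hematologic); 20% relative reduction; correlation 0.3; N = 8,548, taken as 4,274 per arm. Assumed: equal arms and a two-sided 0.05 level, since sidedness is not stated.

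**1. Is the switch condition already met?** Mortality is 0.53% overall and 0.59% under saline, both below 1%. Infection is 23.76 / 0.53, about 45 times mortality. Either limb of the rule is satisfied by the planning figures.

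**2. The stated figure for the alternatives.** Take the lowest possible collapsed rate under saline, 26.40% (infection alone), against 0.8 × 26.40 = 21.12%. The difference is 0.0528 and the SE is √(0.264·0.736/4274 + 0.2112·0.7888/4274) = 0.00919, so z = 5.75 and power exceeds 99.9%. Simulation gives about 99.9% for the common effect test. The protocol's figure of more than 99% reproduces.

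**3. The stated figure for the average relative effect.** The test is a Wald test of the mean of five log odds ratios.
- Log odds ratios for a 20% reduction: −0.224, −0.227, −0.229, −0.292, −0.229; mean −0.240.
- Variance of each, 1/(n·p(1−p)) summed over arms: 0.0897, 0.0276, 0.0207, 0.0026, 0.0191; sum 0.1597.
- Correlation 0: SE = √0.1597/5 = 0.0799, z = 3.01, power 85%.
- Correlation 0.3: adding the covariances raises the sum to 0.3033, so SE = 0.1101, z = 2.18, power 59%. Simulation gives 60%.
- Correlation 0.1: power 75%.

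The 90% does not reproduce from the stated inputs; a one-sided test at correlation 0.3 gives 70%. The macro's settings are not given, and a correlation of 0.3 is not attainable between infection and the rarer components (maximum 0.13 to 0.29 at these rates). This shows that power depends on the test named. It does not prove the sample size wrong.

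**4. Do the tests agree?** Simulated null correlation of the average relative effect and collapsed statistics is about 0.41 to 0.46 with a latent-normal model (0.38 to 0.46 with the other correlation structure tried). In the latter, the common effect statistic correlates 0.86 to 0.96 with the collapsed one and 0.55 to 0.77 with the average relative effect.

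For a 20% reduction in infection only, the mean log odds ratio is −0.292/5 = −0.0585. With SE 0.0755 (correlation 0) to 0.1042 (correlation 0.3), z is 0.77 to 0.56 and power 12% to 9%. Simulations give 10 to 12% (latent-normal) and 8 to 11%. The collapsed composite has over 99%. For a 20% reduction in everything except infection, the order reverses: about 39 to 62% for the average relative effect and 3 to 20% for the collapsed composite.

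**5. Type I error if the alternatives served as a rescue.** For two tests with null correlation r, the error is 1 − P(|Z₁| < 1.96 and |Z₂| < 1.96). At r = 0.41 this is 9.3%; at r = 0.46 it is 9.2%. Allowing any of the three gives 10.0 to 10.5% by simulation. Over four looks at the printed efficacy boundaries, the figures are 9.2 to 9.4% for two tests and 10.2 to 10.7% for three.

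**The case against.** A reader might infer that the protocol permits the test to be chosen after the result, so that the 5% error rate is not held. The documents do not support that. The sentence about insufficiency sits under Sample size and states anticipated power; it is not an analysis instruction. The only explicit switch, in the Primary analysis section, depends on incidence rather than treatment effect, and replaces the first test instead of adding to it. The alpha of 0.05 is assigned to a single primary analysis. Insufficiency may simply refer back to the incidence condition. The 9 to 10% is therefore conditional on one reading.

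It is also fair to say that the wording of the outcome definition may be loose clinical language, since the Primary analysis section openly prefers a multivariate test and explains why. The different power profiles follow from a deliberate choice of weighting, and heterogeneity is to be examined by a treatment-by-component interaction test. The interim test can be guessed from the sample size basis, and an unseen SAP may name it.

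What remains is contradiction, not missing detail. The switch rule is already triggered by the protocol's own table while the sample size assumes it is not. The Sample size section also names a method that the Primary analysis section rejects. An SAP that follows one section departs from another.

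**Conclusion.** The point holds as a failure to fix one primary test. Outcome definition, primary analysis, switch rule and sample size basis do not agree, and the candidates can give different conclusions from the same data. For an infection-only effect, power is roughly 10% with the average relative effect against over 99% with the collapsed composite. At N = 8,548, power for a uniform 20% reduction runs from about 59 to 85% (average relative effect, correlation 0.3 down to 0, two-sided) to about 99.9% or more (common effect, collapsed). An inflated type I error of about 9% (two tests) or 10% (three) would arise only if an alternative were used after a non-significant first result, which the text leaves undefined but does not prescribe. These figures assume equal arms and the protocol's saline incidences.

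**What to change.** Reconcile the Primary outcome, Primary analysis, Interim analyses and Sample size sections:

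1. Name one primary test, either the average relative effect or the common effect GEE. The choice must face the fact that the planning incidences already meet the switch condition.
2. Describe the primary outcome as the five-component vector, and bring the four-item list under Outcomes into line.
3. State that the same test supplies the P value at all four looks.
4. Delete the sentence on insufficiency, or limit it to a single switch decided on pooled, fluid-masked incidences before the first interim analysis, with numerical criteria and never on the test result.
5. Label the collapsed composite and the GEE test not chosen as sensitivity analyses with no claim on the primary alpha.
6. Restate the power at N = 8,548 for the named test, with sidedness and correlation assumptions.

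The edits are mostly wording, but they have a cost. The sponsor gives up a more powerful alternative as a rescue. If the average relative effect is kept, the restated power may fall below 90% and the sample size may have to be reconsidered. If the common effect test is chosen, power is ample, but the result is driven largely by infection and should be described that way.

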5. **Myocardial Injury after Noncardiac Surgery³⁵** – MINS is defined as at least one postoperative value of fourth-generation troponin T ≥ 0.03 ng/ml apparently of ischemic origin, in the 3 days after operation. Eligible patients without postoperative cardiac enzyme determinations will be assumed not to have acute myocardial injury.
6. **Cardiac complication³⁴** – See ICD codes appendix E.

We will exclude following patients from analysis as they have medical conditions that can influence outcomes:

1. Urgent or emergent surgery;
2. ASA physical status 5. That is, patients who are not expected to survive with or without surgery;
3. Chronic renal failure requiring preoperative dialysis;
4. Pulmonary and cardiac surgery – different pathophysiology, and thoracic surgery typically have strict fluid restriction on type and volume of fluid used;
5. Liver resection surgery- strict fluid limits or type and volume of fluids;
6. Surgeries lasting less than 2 hours which typically require small amount of fluids, thus making the type of fluid relatively unimportant.

Data Analysis

Because this trial will not be randomized, we will control for observed potential confounding variables using the inverse propensity score weighting method. We will first fit a multivariate logistic regression model with fluid assignment as the outcome variable and all observed confounding variables as the independent variables. From this model we will estimate propensity scores (i.e., probability of receiving lactated Ringer's solution) for each patient. After weighting observations by their respective inverse propensity score, the success of confounding control will be assessed by comparing groups on potentially confounding baseline characteristics (appendix) using absolute standardized difference (ASD), defined

as the absolute difference in means or proportions divided by the pooled standard deviation. Observations in all primary and tertiary analyses below will be weighted by the inverse of the relevant propensity score. In addition, any confounding variable with an ASD greater than the smaller of 0.2 or $1.96 \times \sqrt{\frac{1}{n_1} + \frac{1}{n_2}}$ will be adjusted for in all analyses.

Primary analysis

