Using the example results above, results would indicate that using intervention B can save 0.2 days, 2 electrolyte measures and an electrolyte replacement equating to \$60 in savings considering only standard care. Incorporating the potential cost savings from avoiding complications, intervention can reduce the incidence of MI, DVT, and pneumonia equating to a potential cost savings of \$800 per patient. For a hospital performing 1,000 procedures a year, using intervention B would potentially save the hospital \$60,000 in standard care costs and \$800,000 costs from avoiding complications.

Using the methods outlined in the example analysis, the analysis will be performed using the relevant outcomes from the clinical trial. The robustness of the results to changes in variable values will be tested using sensitivity analysis. Sensitivity analysis will include one-way and two-way analyses around the baseline values using the confidence intervals derived from the study. Any values where a confidence interval is unknown including cost variables, a 25% range will be used. Any change in values to which the choice strategy is highly sensitive, further sensitivity analysis will be conducted including threshold analysis.

Tertiary outcomes analysis

We will assess the association between fluids and AKIN classification using a multivariable proportional odds model including propensity score weights and adjusting for unbalanced baseline co-variables as appropriate. If AKIN categories have low incidence, we will combine them and perform a multivariable logistic regression analysis instead.

The association of fluids on blood transfusion will be assessed using separate multivariable Poisson or negative binomial regression models for each transfusion type, as appropriate. We will also assess the association of fluids on plasma electrolytes determination using a multivariable Poisson or negative binomial regression model. The association of fluids with the administration of electrolyte replacement and postoperative nausea and vomiting will be assessed through separate multivariable logistic regression models. All above tertiary analyses will adjust for confounding variables that are unbalanced after propensity score weighting.

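### The weighting rule for this non-randomised trial names only primary and tertiary analyses, so nothing states that the secondary economic evaluation is propensity weighted

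*Protocol*

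**What the plan says.** On allocation, the Protocol subsection of Methods is explicit: "Thus, fluid choice will not be randomized on a per-patient or even per-period basis". Data Analysis draws the consequence: "Because this trial will not be randomized, we will control for observed potential confounding variables using the inverse propensity score weighting method". That opening statement is not limited to any tier of outcome.

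The sentence that puts the weights to use is limited: "Observations in all primary and tertiary analyses below will be weighted". The next sentence says that any confounder whose absolute standardised difference exceeds a threshold "will be adjusted for in all analyses". The Primary analysis section adds: "All analyses will adjust for unbalanced potentially confounding baseline characteristics".

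The Outcomes section lists two secondary outcomes: acute kidney injury by AKIN criteria, and the economic evaluation. The AKIN model appears under Tertiary outcomes analysis, with propensity weights named. The Secondary analysis section contains only the economic evaluation. It gives two example tables in which a difference between interventions is multiplied by a unit cost, and says the real analysis will follow that method using the trial's outcomes. Its sensitivity analyses vary the input values over study confidence intervals, or over a 25% range where no interval exists. Weights, regression and confounders are not mentioned.

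**The concern.** In a non-randomised comparison, the weights are the plan's main protection against differences in case mix between saline and lactated Ringer's periods. Three analysis headings follow the weighting sentence, and it names two of them. The one omitted holds the economic evaluation alone.

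An analyst who follows the text literally would weight every clinical comparison and leave the cost comparison unweighted. The cost result is one of two secondary outcomes, and the Objectives section says the Clinic could use it to specify a fluid. Any difference in patient mix that affects length of stay or complications could then be read as a cost effect of the fluid.

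**Working it through.** **1. Which outcomes does the weighting sentence reach?**

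| Outcome | Tier | Weighting stated? |
|---|---|---|
| Composite of major complications | Primary | Yes, by tier |
| Acute kidney injury (AKIN) | Secondary | Yes, in its own model under Tertiary outcomes analysis |
| Economic evaluation | Secondary | No |
| Six tertiary outcomes | Tertiary | Yes, by tier |

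Only the economic evaluation is left out.

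**2. What does the described cost method contain?** The inputs are the example tables in Secondary analysis. The formula is the sum over items of (value in A − value in B) × unit cost.

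- Standard care: 0.2 × 100 + 2 × 10 + 1 × 20 = 20 + 20 + 20 = 60. The protocol gives $60.
- Complications: 0.05 × 10,000 + 0.1 × 1,000 + 0.1 × 2,000 = 500 + 100 + 200 = 800. The protocol gives $800.

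Both totals reproduce exactly from plain differences. The tables do not say how the arm-level values are to be estimated.

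**3. Do the sentences on adjustment in all analyses close the gap?** Data Analysis computes the standardised differences after the observations have been weighted, and the tertiary section confirms the order: "All above tertiary analyses will adjust for confounding variables that are unbalanced after propensity score weighting". The trigger is the smaller of 0.2 and 1.96 × √(1/n₁ + 1/n₂). With the maximum enrolment of 8,548 and equal arms assumed (4,274 each), this is 1.96 × √(2/4,274) = 0.042. A confounder that is imbalanced in the raw data but falls below 0.042 once weighted is not flagged. In an unweighted cost comparison it would be neither weighted nor adjusted for. Nor does the cost calculation, as described, contain a model in which a covariate could be placed.

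**4. Do weighted estimates reach the cost model by another route?** Complications, transfusion, electrolyte determinations, electrolyte replacement, and nausea and vomiting are primary or tertiary outcomes, so their own analyses are weighted. Two difficulties remain.

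- The cost table needs arm-level means and incidences, whereas the planned clinical models (GEE, proportional odds, logistic, and Poisson or negative binomial) give relative effects. Electrolyte replacement is to be modelled by logistic regression, but the example costs it as a count (2 versus 1).
- Length of stay is a named cost input and is not a listed outcome, so no weighted analysis of it exists anywhere.

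**5. Can the size be given?** No. It depends on the raw imbalance and on how strongly the imbalanced variable predicts cost, and the protocol gives neither. To show how open this is, assume 4,274 independent patients per arm, a standardised cost outcome and a 5% two-sided test, with bias = imbalance × effect and SE = √(2/4,274) = 0.0216.

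- Imbalance 0.02, effect 0.1: bias 0.002, or 0.09 SE; false-positive rate about 5%.
- Imbalance 0.20, effect 0.3: bias 0.06, or 2.8 SE; false-positive rate about 79%.

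These inputs are assumptions. The range runs from negligible to dominant, so no figure can be attached to this trial.

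**The case against.** The best defence is that the omission is loose labelling. The opening statement on propensity weighting covers the whole trial, two sentences promise adjustment in all analyses, AKIN is a secondary outcome analysed under the tertiary heading, and the alpha paragraph pools secondary with tertiary. The economic section draws on the trial's outcomes and on study confidence intervals, which may well mean the weighted ones. The example tables use invented values to show arithmetic, not estimation. A statistical analysis plan, not shown here, could settle which estimates enter.

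Much of this stands. A reader might infer three stronger things that the protocol does not support:

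- **That it prescribes a raw cost comparison without covariates.** It never says so, and the sentences on adjustment point the other way.
- **That the report will contain conflicting weighted and crude estimates of the same outcomes.** This is possible but not stated.
- **That the bias in length of stay can be computed from the 0.042 threshold and set against the 0.2 days in the example.** The 0.042 is a trigger applied after weighting, not an estimate of raw imbalance. The 0.2 days is an invented figure (1 minus 0.8), and the protocol gives no standard deviation or correlation for length of stay.

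The defence does not remove the core. The sentence that assigns the weights names its tiers and omits one. The adjustment sentences deal only with what weighting leaves behind, and the second of them sits inside the Primary analysis section. The protocol has fixed the scope in words, so this is more than silence left for a later document to fill.

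**Conclusion.** The point holds as a scoping error with an ambiguity attached. By its wording, the weighting rule excludes the economic evaluation alone, and the economic section does not say which estimates it uses. Length of stay is the clearest uncovered input. Taken literally, the secondary cost result may carry observed confounding that the clinical analyses remove. The amount cannot be stated from the protocol and could be trivial if the alternating periods happen to be well balanced. Confounding by unobserved variables would remain in either case. The conclusion rests on reading the weighting sentence as written and on imbalance being assessed after weighting, which the text supports. No primary result, sample size, power or alpha figure depends on it. It is worth correcting because the result could guide fluid choice and the correction is small.

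**What to change.** In Data Analysis, extend the weighting sentence to *all primary, secondary and tertiary analyses*. In Secondary analysis, add that the arm-level means and incidences entering the cost calculation, including length of stay, and the confidence intervals used in the sensitivity analyses, are propensity weighted and adjusted for residual imbalance in the same way as the clinical outcomes.

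The cost is two sentences and a little extra analysis, chiefly weighted arm-level estimates for length of stay and for items whose clinical models give only relative effects. The weights will already exist. Weighting may widen the intervals slightly, a price the plan already accepts for its other outcomes.
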